# 6.6 Discontinuation of Therapy

Protocol treatment includes both the 6MHP vaccine and ipilimumab. Either or both may be discontinued for any of the following reasons:

Protocol treatment will be discontinued for a participant for any of the following reasons:

 Any dose-limiting toxicity (DLT), as defined in Section 9 warrants discontinuation of the agent to which the DLT is attributed. If a DLT attributed to one intervention is not believed to be related to the other treatment, only the one to which the DLT is attributed must be discontinued. However, management of toxicities attributed to ipilimumab should follow current standard practice guidelines, including use of steroids when indicated.

- Disease progression requiring other therapy (e.g. surgery under general anesthesia, radiation, chemotherapy, or steroid therapy). The appearance of small metastases or recurrent tumor deposits will not be a basis for discontinuing the vaccinations. Biopsy to determine the nature of new lesions, or minor surgical procedures to excise a new lesion, will not be a basis for discontinuing vaccinations. Also, surgery to perform biopsy of tumor at day 22, in accord with the protocol, will not be a basis for discontinuing therapy, whether done under local anesthesia or general anesthesia.
- Initiation of cytotoxic chemotherapy, radiation therapy, or targeted therapy for melanoma or other cancer.
- Initiation of non-permitted medication, or other systemic immunosuppressive therapy, except that steroid or immunosuppressive therapy for management of toxicities of ipilimumab is allowed without discontinuation of vaccines.
- Any other potential adverse reaction deemed sufficiently serious to warrant discontinuation of therapy by the Principal Investigator or one of the Associate Investigators.
- Noncompliance with the requirements of the study.
- Therapy may be discontinued at the participant's request.
- Therapy may be discontinued at the discretion of an Investigator.
- Pregnancy. Pregnant participants will continue to be followed for the duration of the pregnancy.
- Treatment delays as specified in section 6.5.1.

# 6.6.1 Safety follow-up Visits

In the event of an AE, appropriate action will be taken to ensure adequate care for the patient. If the patient is still on protocol, treatment delay or withdrawal from the protocol will be considered according to the protocol guidelines (Section 6.6).

Subjects who discontinue receiving investigational product will begin study-specific follow-up as outlined in Appendix 1. Exceptions for the timing of the follow-up visits include the following:

• Safety follow-up visits may occur prior to the designated time frames for subjects who will begin another cancer therapy and/or for subjects who withdraw consent at the time of discontinuation.

# 6.7 Replacement of Study Participants

A participant who is enrolled but who does not receive study drug or any of the study related procedures may be replaced. Every attempt will be made to evaluate any data from these participants for endpoint assessment.

# 6.8 Concomitant Medications

Medications taken within 30 days prior to registration will be recorded on the baseline case report form. This includes prescription medications, over-the-counter medications, injected medications, biological products, blood products, imported drugs, or street drugs. Participants should be maintained on drugs that they were taking prior to entry unless a change in regimen is medically indicated.

The following are non-permitted medications or treatments

- Cytotoxic chemotherapy
- Interferon therapy (e.g. Intron-A®)
- Radiation therapy
- Nitrosoureas
- Allergy desensitization injections
- Corticosteroids, as detailed in section 3.2.1.
- Growth factors (e.g. Procrit®, Aranesp®, Neulasta®)
- Interleukins (e.g. Proleukin®)
- Antibodies to PD-1 or other immune checkpoint blockade therapies (e.g. Keytruda®)
- Other investigational medications
- Street drugs

# 6.9 **Permitted Medications or Treatments**

- Nonsteroidal anti-inflammatory agents
- Anti-histamines (e.g. Claritin®, Allegra®)
- Topical corticosteroids or steroids for the reasons cited in section 3.2.1 above.
- Short-term therapy for acute conditions not specifically related to melanoma
- Chronic medications except those listed in section 6.8
- Influenza vaccines are permitted, but should be administered at least 2 weeks prior to or at least 2 weeks after a study vaccine.

#### 6.10 Biopsies

For participants with biopsy accessible disease, biopsies (incisional, core or excisional biopsies) of cutaneous, subcutaneous, soft tissue or visceral metastatic melanoma will be obtained:

- at baseline: may be collected previously according to specifications below, during screening or once enrolled, prior to treatment on day 1.
- on day 22: 1 week after the third vaccine.

Biopsies collected previously as part of standard treatment or other protocols may be used as the baseline biopsy provided they meet all of the following:

- a. Sufficient tissue is available
- b. Tissue was collected within 3 months of Day 1
- c. There were no intervening treatments in between the biopsy and the first protocol treatment (dietary supplements are permitted)

Cohort 2 only: oncologic surgery to render patient free of disease on day 22 will provide tissue for day 22 biopsy.

Additional optional biopsies may be performed during active treatment or during follow-up, e.g. for new lesions.

# 7.0 CLINICAL AND LABORATORY EVALUATIONS
The following evaluations will be performed on an outpatient basis. Please refer to the study calendar (Appendix 1) for scheduling.

# 7.1 Physical Exams and Evaluations

- Medical History
- Complete Physical Exam (includes vital signs, weight, performance status, medication review, neurologic function-general)
- Assessment of skin and nodal basins for evidence of disease recurrence or metastasis
- Assessment of skin for vitiligo
- Assessment of hair and eye color
- Designation of vaccination sites (at screening only)
- Visual acuity (Snellen chart) (baseline only)
- Color vision exam (Ishihara eye chart) (baseline only)
- Assessment of baseline symptoms (baseline only)

# 7.2 Pathology Review

• Review of pathology at the University of Virginia

# 7.3 Performance Status

• ECOG performance status criteria will be used in the evaluations (Appendix 3).

# 7.4 Clinical Labs

- CBC with differential, including automated lymphocyte count (0.3 ml)
- Comprehensive chemistry panel to include sodium, potassium, creatinine, glucose, calcium total bilirubin, AST, ALT, and alkaline phosphatase. NOTE: fasting blood sugars, when required, may be evaluated 4 hours or more after last eating. (0.9 ml)
- Lactate dehydrogenase (LDH) (0.3 ml)
- Urinalysis
- β-HCG for women of childbearing potential (2 ml)
- Cortisol (3 ml; combined with TSH and Free T4)
- TSH
- Free T4
- HgB-A1C (3 ml)
- HIV screening (antibody screen); if the antibody screen is positive, follow-up testing by RNA analysis may be completed to determine whether active disease is present. (3 ml)
- HCV screening (antibody screen); if the antibody screen is positive, follow-up testing by RNA analysis may be completed to determine whether active disease is present. (combined with HIV)
- Anti-nuclear antibody and rheumatoid factor (4 ml)

# 7.5 **Toxicity Assessments**

- Assessment of adverse events. The NCI Common Terminology Criteria for Adverse Events (CTCAE) version 4.03 will be used for the characterization and grading of adverse events.
- Toxicity diaries will be distributed to participants and reviewed by study personnel.

# 7.6 Research Blood Samples

Blood should be obtained prior to the vaccine injection if a vaccine is scheduled to be administered. Results of research blood tests are not required prior to administering the vaccine on that date.

- The following blood samples for research will be collected and processed by the UVA Biorepository and Tissue Research Facility (BTRF).
  - 80 cc -120 cc blood collected in heparinized green top tubes for lymphocytes.
  - 20 cc blood collected in red top tubes for serum

# 7.7 Tumor Biopsies

Tumor biopsies will be completed in participants with adequate and accessible metastatic tumor in addition to measurable disease.

# 7.7.1 Size Requirements

A critical component of this protocol is the histologic and cytologic evaluation of changes in immune effectors and the tumor microenvironment after vaccination and systemic therapy. A minimum of 0.1 cm^3 and up to about 0.3 cm^3 of tissue will be needed for each biopsy time point as described in the inclusion criteria. Biopsies may be taken from a single lesion or multiple lesions at each of the time points depending on the size of each lesion.

# 7.7.2 Sampling

The biopsies will vary based on the clinical scenario and may include five core biopsies, an incisional biopsy or an excisional biopsy as outlined in the inclusion criteria.

# 7.7.3 Procedure

When appropriate (and we anticipate the majority of cases) the biopsies will be performed under local anesthesia (typically lidocaine HCl 1% and epinephrine 1:100,000 injection + or - 8.4% sodium bicarbonate), in the outpatient clinic or comparable procedure room, using sterile technique. In cases when clinical standard of care requires a larger procedure the biopsies may be performed in the operating room under standard technique.

To minimize errors in analysis due to sampling error and specimen heterogeneity, each study biopsy specimen will be divided into several components and randomly allocated into various preservation conditions when possible:

- a. 20% (1/5 of single biopsy or 1 core biopsy) will be fixed in formalin, then paraffin-embedded (for histology/immunohistology)
- b. 20% (1/5 of single biopsy or 1 core biopsy) will be processed for protein studies

- c. 40% (2/5 of single biopsy or 2 core biopsies) will be processed for single- cell suspension by mechanical disaggregation, then enzymatic digestion (collagenase, hyaluronidase, DNAase). The resulting suspensions will be cryopreserved in FBS serum and DMSO (for cellular immune function and flow cytometry).
- d. 20% (1/5 of single biopsy or 1 core biopsy) will be placed in RNA-later (for RNA/RT PCR)
- e. If there is additional tissue, it may be processed for additional immunologic or angiogenic studies.

The incisions will be sutured closed.

Toxicities related to the biopsies will be recorded.

#### 7.7.4 Evaluations

- a. Tissue samples may be screened for antigen expression or protein profiles using tests such as Western blots, immunohistochemistry, PCR, flow cytometry or gene chip analysis.
- b. Tumor escape mechanisms may also be evaluated.
- c. Specimens will be used in immunological assays to assess T cell function or antibody response. Assays generally used for this type of testing include, but are not limited to, ELIspot assays, ELISAs, chromium-release assays, proliferation assays, intracellular cytokine staining, and T cell receptor sequencing.
- d. Specimens may be used to study the immunologic aspects of the tumor microenvironment or as targets or controls in laboratory assays.
- e. Specimens may be used to establish cell lines for long-term studies.
- f. This tissue may also be compared to lesions resected prior to enrollment, which will be requested from the pathology department of each institution as paraffin-embedded tissue samples, and these tissues may be banked for use in future studies.
- g. HLA typing (Class I and Class II) will be analyzed as part of the immunologic endpoints. (8 ml)
- 7.7.5 Optional Tumor Biopsies (at the time of progression, after study completion and withdrawal)

If during the study, participants develop superficial metastatic deposits accessible to biopsy/excision with minimal morbidity, an optional biopsy may be collected for research purposes.

If tumor samples are collected when a Mel 62 participant is no longer participating in the Mel 62 study and the participant consents to allow their tissue to be collected under the IRB #10598 tissue banking study to be analyzed for Mel 62, the tissue may be analyzed as part of the Mel 62 analysis.

Optional biopsy samples may be evaluated as described in section 7.7.4.

# 7.7.6 Tumor Collected for Clinical Care

If during the study, participants develop metastases or recurrences, or progress, these may be removed as part of their clinical care, and following receipt by pathology, may be evaluated by the study research team.

# 7.8 Sentinel Immunized Node Biopsy

# 7.8.1 Procedure

The node (sentinel immunized node, SIN) will be identified by radiocolloid (usually technetium 99 sulfur colloid) injection, with or without lymphoscintigraphy imaging, and with use of a handheld gamma probe during the procedure. This will be performed under local anesthesia in the clinic, in conjunction with the vaccine site biopsy, by a qualified surgeon. Lymphatic mapping will be initiated, usually in the nuclear medicine suite, after intradermal injection with radiocolloid (typically technetium 99-sulfur colloid). The node excision will be performed under local anesthesia (usually lidocaine HCI 1-2%, with or without epinephrine 1:100,000 injection, with or without 8.4% sodium bicarbonate), in the outpatient clinic or comparable procedure room, using sterile technique. A handheld gamma probe will be used.

When possible, the node will be sectioned into 5 sections: a central section (10-20% of the node), leaving two adjacent sections of about 40% each. These latter two sections will be bisected. They will be allocated into various preservation conditions:

- a. 1 central section will be fixed in formalin, then paraffin-embedded (for histology/immunohistology)
- b. 1 section will be placed in RNA-later. (for RNA/RT PCR)
- c. 1 section will be quick-frozen (for immunohistology/protein studies)
- d. 2 sections (40%) will be processed for single cell suspension by mechanical disaggregation, then enzymatic digestion (collagenase, hyaluronidase, DNAase). The resulting suspensions will be cryopreserved in FBS and DMSO (for cellular immune function and flow cytometry).

# 7.9 Assessments

7.9.1 Anti-tumor Activity

Anti-tumor activity will be assessed by the following:

# Tumor Imaging

Tumor imaging may include CT/PET-CT scans and/or MRI. These will complement physical exam and other imaging as required, but the primary measures of clinical response will be based on CT/PET-CT and/or MRI. For each participant, the same method of assessment will be used to evaluate tumor burden at baseline and throughout the course of the study.

#### Tumor Measurments

RECIST 1.1 Criteria will be used to evaluate tumor burden. These are summarized in Appendix 5 (58)

#### 7.9.2 Immunologic Assessments

Assessments of T cell function may include, but are not limited to the following:

- ELIspot assays
- ELISAs
- Chromium-release assays
- Proliferation assays
- Intracellular cytokine staining
- T cell receptor sequencing.
- Cytokine bead array
- Flow cytometry
- HLA typing

Characterization of cellular populations may include, but are not limited to the following:

- Immunohistochemistry
- Gene expression analysis
- Flow cytometry
- ELISAs
- Western-blot analysis
- Intracellular cytokine staining
- Cytokine bead array

# 7.10 Study Calendar

(See Appendix 1)

# 8.0 STATISTICAL CONSIDERATIONS

#### 8.1 Design

This is an early phase trial to evaluate whether the combination of the 6MHP vaccine with CTLA-4 blockade ipilimumab will be safe and will result in a CD4+ T cell response to 6MHP peptides. The combination will be assessed in three clinical cohorts: advanced disease, neoadjuvant therapy and adjuvant therapy. The trial should provide preliminary information on the disease control rate of the combination in the advanced setting as well as the recurrence risk and time to recurrence in the neoadjuvant and adjuvant settings. The primary goals are to assess safety and to determine if magnitude of immune response to the 6MHP vaccine can be improved by the addition of anti-CTLA-4.

#### 8.2 Evaluation of Sample Populations and Criteria

8.2.1 Safety

All participants receiving any protocol treatment will be evaluated for safety.

The 6MHP vaccine has been safe, with lower toxicities than with class I peptides, in particular with lower autoimmune or hyperimmune toxicities. Ipilimumab causes toxicities related to unmasking autoimmunity, some of which can be severe, but are managed well with steroids. We do not

anticipate increased autoimmune toxicities by combining 6MHP vaccine with ipilimumab, but relatively high rates of hypophysitis have been reported by combining ipilimumab with each of two other vaccines. Thus, this trial will be designed with stopping rules for toxicities beyond those expected with ipilimumab alone. Formal safety bounds (Section 8.5) based upon monitoring dose limiting toxicities (DLT) will guide decisions about early stopping due to potential safety concerns. If a stopping bound is crossed then accrual to the study will be suspended until the study PI, co-investigators and the DSMC can review the data, and determine if the study should continue, be amended or be closed to further accrual. The proposed safety bound will be applied overall and within cohort.

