### 6.5.2 Delayed Visits for Reasons Other Than Toxicity

A schedule for return visits should be established at the first visit. If a participant misses a treatment, the missed treatment will be administered as soon as possible, so that subsequent treatments will be given in the appropriate intervals. Treatment may be continued for an additional time period, if needed. Participants who are treated outside of the established schedule should return to the original schedule as soon as possible

The table below (Table 7) defines what constitutes a delayed visit, whether the participant should continue to be treated, and whether a protocol violation should be reported and recorded. The range of days is counted from the original scheduled date.

Table 7. Delayed Visit for Reasons other than Toxicity				
Treatment Period	Range of Days	Participant Treatment	Protocol Deviation	
Vaccine 1*/Ipilimumab 1				
Day 1	± 2 days	Vaccine, Labs, Ipilimumab	No	
	$\pm$ 3 to 7 days	Vaccine, Labs, Ipilimumab	Yes	
	$\pm$ 8 or more days	Labs	Yes	
Vaccines 2-3*				
Days 8, 15	± 2 days	Vaccine/Labs	No	
	$\pm$ 3 to 7 days	Vaccine/Labs	Yes	
	$\pm$ 8 or more days	Labs	Yes	
Biopsy/Ipilimumab 2				
Day 22	± 2 days	Labs, Biopsies, Ipilimumab	No	
	$\pm$ 3 to 7 days	Labs, Biopsies, Ipilimumab	Yes	
	$\pm$ 8 or more days	Labs	Yes	
Vaccine 4*/Ipilimumab 3				

Davs 43	± 2 days Vaccine, Labs, Ipilimuma		No
	$\pm$ 3 to 7 days	Vaccine, Labs, Ipilimumab	Yes
	± 8 or more davs	Labs	Yes
Assessment			
Day 57	±7 days	Scans**	No
	$\pm$ 8 to 14 days	Scans	Yes
	$\pm$ 15 or more days	Scans	Yes
Vaccine 5*/Ipilimumab 4			
Day 64	± 7 days	Vaccine, Labs, Ipilimumab	No
	$\pm$ 8 to 14 days	Vaccine, Labs, Ipilimumab	Yes
	$\pm$ 15 or more days	Labs	Yes
Vaccine 6*			
Day 85	± 7 days	Vaccine, Labs, Scans**	No
	$\pm$ 8 to 14 days	Vaccine, Labs, Scans**	Yes
	$\pm$ 15 or more days	Labs/Scans	Yes
Assessment			
Day 92	± 7 days	Labs	No
	$\pm$ 8 to 14 days	Labs	Yes
	$\pm$ 15 or more days	Labs	Yes
Follow-up			
FUv1 and FUv2	± 14 days	Labs/Scans**	No
	$\pm$ 15 or more days	Labs/Scans	Yes
– "			ļ
Follow-up			
FUv3, FUv4, FUV5	$\pm$ 28 days	Labs/Scans**	No
	$\pm$ 29 or more days	Labs/Scans	Yes

\* A participant will be taken off protocol treatment if more than one vaccination is delayed [± 3 to 7 days] during the treatment period.

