#### 9.4.2 Time Span for Reporting Adverse Events

Reporting of AEs will begin when the participant is administered the study drug or has a study related biopsy. Events occurring through 30 days after administration of the last dose of 6MHP vaccine or ipilimumab, regardless of attribution, will be reported. AEs should be followed to resolution or stabilization. If an AE worsens and becomes an SAE, it should be reported as serious per the guidelines specified for SAE reporting.

AEs that are possibly, probably, or definitely related to any of the study drugs will be recorded until the participant completes treatment follow-up. If, during treatment follow-up, the participant receives an alternative anti-cancer treatment, participants will be off treatment follow-up and will be followed yearly for disease progression and survival.

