# **Ipilimumab**

A DLT of ipilimumab is defined as any toxicity that is definitely, probably, or possibly related to the administration of ipilimumab and requires permanent discontinuation of ipilimumab.

If a DLT occurs and cannot be attributed to either the 6MHP or ipilimumab, then a DLT will be attributed to both.

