# Appendix 1: Study Calendar

			Active Treatment							Follow-up m						
Studies & Tests	At	Day	1	8	15	22	43	57	64	85	92	FU	FU	FU	FU	FU
	Screening	Week	0	1	2	3	6	8	9	12	13	18	24	27	V4 52	104
Informed consent	Xa															
Pathology review	Xa															
CBC with differential	Xp		Xf			Х	Х		Х	Х					Х	Х
Comprehensive chemistry	X b,e		Xf			Х	Х		Х	Х					Х	Х
HGB-A1C	Xp															
LDH	Xp															
Cortisol			Х			Х	Х		Х							
Free T4			Х			Х	Х		Х							
TSH			Х			Х	Х		Х							
Urinalysis	Xb															
β-HCG	Xc															
HIV / Hepatitis C	Xd															
CT chest/abdomen/pelvis or PET-CT	Xp							х		X h		Xi		х	Xj	Xj
Head MRI / CT	Xp							XI		X h		Xi		Х	Xj	Xj
History & physical	Xp		Xf	Х	Х	Х	Х		Х	Х	Х	Х	Х	Х	Х	Х
Medication Review	Xp		Х	Х	Х	Х	Х		Х	Х	Х	X n	Xn	Xn	Xn	Xn
Record baseline symptoms			Х													
AE assessment				Х	Х	Х	Х		Х	Х	Х	Х	Х	Х	Х	Х
Designation of potential vaccination sites	Xp															
Assessment of skin and nodal basins for evidence of disease	Xp									х				х	х	х
Assessment of skin for vitiligo			Х			Х				Х				Х	Х	Х
Assessment of hair and eye color			Х			Х				Х				Х	Х	Х
Visual acuity exam/ color vision			Х													
120cc green top tubes			X k													
80cc green top tubes				Х	Х	Х	Х		Х	Х	Х	Х	Х	Х	Х	Х

			Active Treatment									Follow-up m				
Studies & Tests	At Screening	Day	1	8	15	22	43	57	64	85	92	FU v1	FU v2	FU v3	FU v4	FU v5
		Week	0	1	2	3	6	8	9	12	13	18	24	27	52	104
20cc red top tubes			Х	Х	Х	Х	Х		Х	Х	Х	Х	Х	Х	Х	Х
Anti-nuclear antibody / Rf factor			Х						Х						Х	Х
Vaccination with 6MHP			Х	Х	Х		Х		Х	Х						
Tumor biopsy g			Х			Х										
Sentinel immunized node biopsy						Х										
Participant diary reviewed and/or distributed			х	х	х	х	х		х	х	х	Х				
ipilimumab: 3 mg/kg IV			Х			Х	Х		Х							

a Any point prior to registration

b Pre-study within 6 weeks of registration

c Within 2 weeks of registration (for childbearing women)

d Within 6 months of registration

e To include fasting glucose

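### No cortisol, TSH or free T4 is scheduled after the last ipilimumab dose, so symptom-free or mild endocrine irAEs after that point may go unrecorded

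*Combined protocol and SAP*

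**What the plan says.** **The stated worry.** Section 8.2.1 does not expect more autoimmune toxicity from the combination, but adds that "relatively high rates of hypophysitis have been reported by combining ipilimumab with each of two other vaccines" and gives this as the reason for stopping rules. Safety is a primary objective, broken down by irAE category (section 2.1). Section 8.6 tabulates adverse events by how often and how severely they occur.

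**The schedule.** Section 7.4 lists cortisol, TSH and free T4 as clinical labs, and section 7.0 refers to Appendix 1 for timing. The three hormone rows there carry marks in the same four columns as the row "ipilimumab: 3 mg/kg IV".

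**The recording period.** Section 9.4.2 sets two windows. For all events: "Events occurring through 30 days after administration of the last dose of 6MHP vaccine or ipilimumab, regardless of attribution, will be reported". For related events: "AEs that are possibly, probably, or definitely related to any of the study drugs will be recorded until the participant completes treatment follow-up". Section 6.1 ends treatment follow-up at 24 months, or earlier if another therapy starts.

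**Early stopping.** Section 6.6 lets the agents stop separately: if a DLT is thought unrelated to the other treatment, "only the one to which the DLT is attributed must be discontinued". Section 6.6.1 says: "Subjects who discontinue receiving investigational product will begin study-specific follow-up as outlined in" Appendix 1, where the follow-up visits contain no hormone tests.

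**The concern.** The plan names one endocrine toxicity as a worry for this combination, then stops scheduling the tests for it on the day of the last infusion. Other autoimmune checks continue: skin and hair pigment at day 85 and FUv3 to FUv5, and ANA with rheumatoid factor at FUv4 and FUv5. No reason is given for the difference.

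Two things are at stake. The first is how complete the primary safety description is. Table 5, the plan's own ipilimumab reference, counts hormone changes alone (raised thyrotropin, lowered corticotropin) as irAEs. After day 64 such a change enters the tabulation only if someone happens to order the test. The second is the participant's interest in having a hormone deficit found before it causes symptoms.

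**Working it through.** The plan states no figure here to reproduce. The check compares calendar rows and does day arithmetic.

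**1. Rows of Appendix 1**

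| Row | Marked at |
|---|---|
| Cortisol, free T4, TSH | days 1, 22, 43, 64 |
| Ipilimumab | days 1, 22, 43, 64 |
| 6MHP vaccine | days 1, 8, 15, 43, 64, 85 |
| Comprehensive chemistry | screening, days 1, 22, 43, 64, 85, FUv4, FUv5 |
| AE assessment | days 8, 15, 22, 43, 64, 85, 92, FUv1 to FUv5 |

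Scheduled hormone panels after day 64: none. Table 7 lists unspecified labs at later visits but names no hormone. If the day-64 sample is drawn before the infusion, it reflects three doses, not four. That order is an assumption, because section 7.6 fixes it only for research blood before a vaccine.

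**2. Length of the unscreened period for completers**

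- All-attribution window: 85 + 30 = day 115, so 115 − 64 = 51 days follow the last panel.
- Related-event window: to about day 730, so 730 − 64 = about 666 days follow it. With a day-85 panel this becomes 730 − 85 = about 645.

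Endocrine irAEs are treatment-related, so the second window is the relevant one. Neither figure measures risk.

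**3. Where a day-85 panel falls after dose 4**

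Nominally 85 − 64 = 21 days. Table 7 allows ±7 days at both visits without a deviation, and "The range of days is counted from the original scheduled date". The range is therefore (85 − 7) − (64 + 7) = 7 days to (85 + 7) − (64 − 7) = 35 days.

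**4. Why FUv1 cannot simply stand in for day 85**

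Footnote m times FUv1 at 42 days after the last vaccine, not the last infusion. On nominal days:

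- Completers: 85 + 42 = day 127, which is 63 days after dose 4.
- Both agents stopped early together: 35 days after the last infusion (dose 2, last vaccine day 15: 57 − 22) to 56 days (dose 1, last vaccine day 15: 57 − 1).
- Vaccine last given day 15, ipilimumab last given day 43: FUv1 is day 57, only 14 days after.
- Ipilimumab last given day 1, vaccine last given day 43: FUv1 is day 85, 84 days after.

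**5. Scale, over the whole ipilimumab course**

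The Table 5 rows that match a symptom-free finding are increased thyrotropin (3 of 511) and decreased corticotropin (2 of 511). With full overlap this is 3/511 = 0.6%; with none, 5/511 = 1.0%. For 27 participants: 27 × 3/511 = 0.16 to 27 × 5/511 = 0.26. An unknown share would arise after the last dose. The higher rate reported with other vaccines is not given, so these figures may not carry over to the combination.

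**The case against.** The strongest reply is that the plan answers the hypophysitis worry with stopping rules and nowhere promises hormone screening after treatment. Detection does continue. AE assessment and history and physical take place at day 85, day 92 and every follow-up visit. Section 9.7.1 asks about headache, fatigue, visual change and appetite. Chemistry is drawn at day 85, FUv4 and FUv5. Section 9.8 records relevant results obtained in routine care, and sections 6.4.2 and 9.10 defer to standard practice and the package insert, which may themselves call for hormone tests. Expected numbers are small, and extra testing weakens any comparison with historical rates.

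Most of this stands, and it sets the limits of the point. It does not close the gap. The deferral to standard care concerns managing toxicity, and the documents do not say that it includes hormone tests after the last dose. A symptom-free change still depends on someone ordering the test.

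A reader might infer that hypophysitis after day 64 would go undetected. The documents do not support that, because symptomatic cases have several routes to detection. A reader might also infer that the stopping rule is compromised. An ipilimumab DLT is one that "requires permanent discontinuation of ipilimumab", and completers have no dose left after day 64. A vaccine DLT needs an unexpected event of grade 3 or worse, which a symptom-free or mild change would seldom be (a clinical judgement).

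**Conclusion.** The mismatch between section 8.2.1 and Appendix 1 is real: completers have no scheduled hormone panel after dose 4 or after vaccine 6. Participants who stop all treatment early may also lack one after their last infusion. Those who stop ipilimumab but stay on vaccine would, on a plain reading, keep the remaining calendar panels.

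The consequence is limited to scheduled detection of symptom-free or mild endocrine irAEs. No planned analysis is invalidated, and the DLT rule would rarely change. It would be wrong to read the 51 or 666 uncovered days as a proportion of cases missed: the documents give no onset times and no rate for the combination, so that number cannot be estimated. The change is still worth making because it is cheap and improves both the primary safety description and participant care. The conclusion assumes that Appendix 1 is the full schedule and that standard care is not already known to supply these tests.

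**What to change.** - **Day 85.** Add cortisol, TSH and free T4 to the existing clinical draw.
- **No day-85 visit.** Draw the panel at the first scheduled visit at least about 3 weeks after the last ipilimumab dose, whatever the date of FUv1.
- **Optional.** Add a panel at FUv1 for everyone. It would be the first after vaccine 6, since day 85 is itself the day of vaccine 6. It would also cover a participant whose FUv1 comes too soon to meet the 3-week rule.
- **Reporting.** For each endocrine irAE, record whether a scheduled panel or a clinical work-up found it, so that any informal comparison with Table 5 can be interpreted.

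No dosing or treatment rule changes.

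**Cost.** At most 27 × 1 = 27 panels, or 27 × 2 = 54 if FUv1 is added for all. Each is one 3 ml tube (section 7.4) beside 80 + 20 = 100 cc of research blood already drawn that day, so 3% more. Day 85 already has clinical labs; FUv1 has only research blood and would need a clinical tube. Some incidental findings will need work-up, and the detected rate may exceed Table 5 because of more testing.
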